#### **10.2.2.2 Visit 3 (First Month in Clinic, $\pm 3$ Days)**

At Visit 3, subjects should return to the study site and the following assessments will be completed:

- Conduct urine drug screen (Instant Exam, to be performed on site, with results documented in the source. If urine drug screen result is positive [REDACTED], then urine sample will be sent to central laboratory for confirmation as needed). If the urine drug screen is confirmed as positive, a repeat unscheduled urine drug screen may be obtained to investigate whether drug use is continuing. The Medical Monitor should be consulted regarding these cases.
- For females of childbearing potential, obtain urine sample and complete on-site urine pregnancy test
- Record concomitant medication use
- Administer the LSAS
- Administer the HAM-D17
- [REDACTED]
- Administer the C-SSRS (Since Last Visit)
- Perform focused physical examination, including body weight (pounds). The physical examination includes a review of the nasal passages and oropharynx but other organ systems should be examined only if the subject has symptoms or the investigator is concerned.
- Measure vital signs after the subject has rested for 5 minutes: seated systolic and diastolic blood pressure, heart rate, respiratory rate, and body temperature (°F)
- Obtain 12-lead ECG in supine position after the subject has rested for 5 minutes
- Obtain blood and urine samples for evaluation by the central clinical laboratory, including hematology, chemistry, thyroid functioning, and urinalysis (refer to Section 10.3.1.1.1 for complete list)
- Complete the CGI-S with a recall period of 1 week (by the trained clinician)
- Complete the CGI-I as compared to baseline visit (Visit 2), with a recall period of 1 week (by the trained clinician)
- Complete the PGI-C as compared to baseline visit (Visit 2), with a recall period of 1 week (by the subject)
- Dispense study medication and provide the subject with the storage instructions of the IP (1-month supply of IP)

- Review and record AEs
- Review the use of IP and any health problems they experienced as reported in the eDiary (by study staff)

#### **10.2.2.3 Visit 4 Through Visit 13 (Monthly Visits, ±7 Days)**

At Visit 4 through Visit 13, study assessments will be the same as those conducted at Visit 3 (see Section 10.2.2.2). Visits 4 through 13 will be conducted on a monthly basis, with a ±7-day window.

#### **10.2.3 Visit 14 End of Treatment (or Early Termination) Visit**

At Visit 14, subjects should return to the study site for an End of Treatment visit, and undergo the assessments shown in the schedule of events.

In addition, subjects who discontinue from the study early (for any reason other than loss to follow-up) should return to the study site for an Early Termination Visit. Similarly, if the subject is attending a scheduled visit when the decision to discontinue is made, the investigator should perform the assessments indicated for Visit 14/Early Termination Visit in the schedule of events (Table 2-1).

The following assessments will be completed at Visit 14/Early Termination:

- Record concomitant medication use
- Obtain blood and urine samples for evaluation by the central clinical laboratory, including hematology, chemistry, thyroid functioning, and urinalysis (refer to Section 10.3.1.1.1 for complete list)
- Conduct urine drug screen (Instant Exam, to be performed on site, with results documented in the source. If urine drug screen result is positive [REDACTED], then then urine sample will be sent to central laboratory for confirmation as needed).
- For females of childbearing potential, obtain urine sample and complete on-site urine pregnancy test
- Obtain 12-lead ECG in supine position after the subject has rested for 5 minutes
- Perform physical examination, including height (inches) and body weight (pounds). Also includes an examination of the nasal passages
- Measure vital signs after the subject has rested for 5 minutes: seated systolic and diastolic blood pressure, heart rate, respiratory rate, and body temperature (°F)
- Administer the LSAS
- Administer the HAM-D17
- [REDACTED]
- Administer the C-SSRS (Since Last Visit)
- Complete the CGI-S with a recall period of 1 week (by the trained clinician)

- Complete the CGI-I as compared to baseline visit (Visit 2), with a recall period of 1 week (by the trained clinician)
- Complete the PGI-C as compared to baseline visit (Visit 2), with a recall period of 1 week (by the subject)
- Complete PWC-20
- Review the use of IP and any health problems they experienced as reported in the eDiary (by the trained clinician)
- Review and record AEs (by the trained clinician)

#### **10.2.4 Visit 15 (Follow-up, 54 weeks ±3 Days)**

At Visit 15, subjects should return to the study site and the following assessments will be completed:

- Measure vital signs after the subject has rested for 5 minutes: seated systolic and diastolic blood pressure, heart rate, respiratory rate, and body temperature (°F)
- Administer C-SSRS (Since Last Visit)
- Complete PWC-20
- Review and record AEs

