	
Subjects will return to the clinic at monthly intervals (<math>\pm 7</math> days, Visits 4 to 13), and will repeat the same assessments as those performed at Visit 3. PH94B use and any daily reports of health problems that have been recorded in the eDiary application will be reviewed, AEs and concomitant medications will be reported and recorded. Subjects will receive a 1-month supply of PH94B at each monthly visit.

	
At Visit 14 (12 months <math>\pm 2</math> weeks), treatment will conclude, and subjects will undergo clinical laboratory assessments (clinical chemistry, hematology, urinalysis, pregnancy test, and urine drug screening), vital signs, 12-lead ECG, physical examination, HAM-D17, HAM-A, LSAS, C-SSRS, CGI-S, CGI-I, PGI-C, and the Penn Physician Withdrawal Checklist (PWC-20). Also, PH94B use and any daily reports of health

	
problems that have been recorded in the eDiary application will be reviewed and AEs and concomitant medications will be recorded and reported. Subjects will also be informed of their follow-up visit (Visit 15).
 
Subjects will return to the clinic for a follow-up visit (Visit 15, 54 weeks <math>\pm</math>3 days), approximately 2 weeks after the last PH94B administration, to undergo C-SSRS, PWC-20, and vital signs assessments, and record AEs.
 
Subjects who discontinue study treatment without completing 12 months of treatment will attend an Early Termination Visit (Visit 14) as soon as possible after discontinuing treatment, and return to the clinic for a follow-up visit (Visit 15) approximately 2 weeks later.
 
Safety Considerations:
 
Safety and tolerability of PH94B (<math>\leq</math> 4 doses per day up to 12 months in up to 600 subjects) will be assessed and summarized through changes from Visit 2 (Baseline) to end of treatment (Visit 14) in AEs, laboratory values, 12-lead ECGs, physical examinations, suicidality, level of depression, vital sign assessments, and withdrawal symptoms following exposure to PH94B.

PLANNED NUMBER OF SUBJECTS	A sufficient number of subjects from previous PH94B SAD studies will be screened or rolled over to obtain up to 600 subjects to receive up to 12 months of PH94B treatment.

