## 2.2. Schedule of Events

Table 2-1: Schedule of Events

Assessment/Evaluation	Study Periods					
	Visit 1	Visit 2	Visit 3	Visits 4 to 13	Visit 14 / ET	Visit 15
	Screening	Baseline	1st Month	Monthly	End of Treatment	Follow-up
	[REDACTED]	[REDACTED]	[REDACTED]	[REDACTED]	[REDACTED]	[REDACTED]
Informed Consent Form	X a	X a				
Subject Demographics	X					
Urine Drug Screen	X	X	X	X	X	
Pregnancy Test b	X	X	X	X	X	
MINI 7.0.2	X					
Medical and Psychiatric History	X					
Record Concomitant Medication Use	X	X	X	X	X	
[REDACTED]	[REDACTED]					
LSAS	X	X	X	X	X	
HAM-D17 [REDACTED]						
C-SSRS	X	X	X	X	X	X
Physical Examination c,d	X	X	X	X	X	
Vital Signs	X	X	X	X	X	X
12-Lead Electrocardiogram e	X	X	X	X	X	
Clinical Chemistry, Hematology, and Urinalysis	X	X	X	X	X	
Review Inclusion/Exclusion Criteria	X	X f				
CGI-S	X	X	X	X	X	
CGI-I			X	X	X	
PGI-C			X	X	X	
PWC-20					X	X

Assessment/Evaluation	Study Periods					
	Visit 1	Visit 2	Visit 3	Visits 4 to 13	Visit 14 / ET	Visit 15
	Screening	Baseline	1st Month	Monthly	End of Treatment	Follow-up
	Day -35 to Day -7	Day 0	Day 30 ±3 days	±7 days	52 Weeks ±2 weeks	54 Weeks ±3 days
Training on Use of PH94B		X				
Storage Instructions		X	X	X		
Training on eDiary App to Record PH94B Use and Health Problems		X				
Adverse Event Recording		X	X	X	X	X
Dispense PH94B to Subject		X	X	X		
eDiary Review			X	X	X	

Abbreviations: C-SSRS = Columbia-Suicide Severity Rating Scale; CGI-I = Clinical Global Impression Scale of Improvement; CGI-S = Clinical Global Impression Scale of Severity; eDiary = electronic diary; ET = Early Termination; HAM-A = Hamilton Rating Scale for Anxiety; HAM-D17 = Hamilton Rating Scale for Depression (17 items); LSAS = Liebowitz Social Anxiety Scale; MINI = Mini-International Neuropsychiatric Interview; PGI-C = Patient Global Impression of Change; PWC-20 = Penn Physician Withdrawal Checklist; SAD = social anxiety disorder

- a Subjects will sign an informed consent form for the present study at either Visit 1 or Visit 2, depending on when they enter the study.
- b Pregnancy tests will only be given to female subjects of childbearing potential and not post-menopausal females.

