Subjects will be instructed to return to the clinic for Visit 3 after 30 days ( $\pm 3$  days). At Visit 3, subjects will undergo clinical laboratory assessments (clinical chemistry, hematology, urinalysis, pregnancy test, and urine drug screening), vital signs, 12-lead ECG, physical examination (limited to nasal passage and oropharynx examination unless any AEs are reported), HAM-D17, [REDACTED] LSAS, C-SSRS, CGI-S, CGI-I, and self-evaluation by the patient-reported outcome measure, Patient Global Impression of Change (PGI-C). At Visit 3, PH94B use and any daily reports of health problems that have been recorded in the eDiary application will be reviewed and AEs and concomitant medications will be reported and recorded. Subjects will receive a 1-month supply of PH94B.

Subjects will return to the clinic at monthly intervals ( $\pm 7$  days, Visits 4 to 13), and will repeat the same assessments as those performed at Visit 3. PH94B use and any daily reports of health problems that have been recorded in the eDiary application will be reviewed, AEs and concomitant medications will be reported and recorded at each visit. Subjects will receive a 1-month supply of PH94B at each monthly visit.

At Visit 14 (12 months $\pm$ 2 weeks), treatment will conclude, and subjects will undergo clinical laboratory assessments (clinical chemistry, hematology, urinalysis, pregnancy test, and urine drug screening), vital signs, 12-lead ECG, physical examination, HAM-D17, [REDACTED] LSAS, C-SSRS CGI-S, CGI-I, PGI-C, and the Penn Physician Withdrawal Checklist (PWC-20). Also, PH94B use and any daily reports of health problems that have been recorded in the eDiary application will be reviewed, and AEs and concomitant medications will be recorded and reported. Subjects will also be informed of their follow-up visit (Visit 15).

Subjects will return to the clinic for a follow-up visit (Visit 15, 54 weeks  $\pm$ 3 days), approximately 2 weeks after the last PH94B administration, to undergo C-SSRS, PWC-20, and vital signs assessments, and record AEs.

Subjects who discontinue study treatment without completing 12 months of treatment will attend an Early Termination Visit (Visit 14) as soon as possible after discontinuing treatment, and return to the clinic for a follow-up visit (Visit 15) approximately 2 weeks later.

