## 10.1. Study Duration

The study comprises a 7- to 35-day screening period and a treatment period of up to 12 months, and a follow-up visit at 2 weeks after the last visit.

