## 10.2. Study Periods and Visits

A comprehensive schedule of study assessments is presented in [Table 2-1](#) and described in the following sections. Every effort should be made to complete all required procedures and evaluations at the designated visits. A window of  $\pm 3$  days is permitted for Visit 3 and the follow-up visit (Visit 15), with a window of  $\pm 7$  days permitted for Visits 4 through 13, and  $\pm 2$  weeks for Visit 14.

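### For subjects who complete treatment, the week-54 window for Visit 15 cannot be reconciled with a follow-up two weeks after Visit 14 unless Visit 14 falls close to Day 364

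*Protocol*

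**What the plan says.** The protocol gives three anchors for Visit 15 in subjects who finish 12 months of treatment.

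- **Calendar.** The Schedule of Events (Section 2.2) puts Visit 14 at "52 Weeks ±2 weeks" and Visit 15 at "54 Weeks ±3 days". The Section 10.2.4 heading repeats the second: "Visit 15 (Follow-up, 54 weeks ±3 Days". The Synopsis, Section 7.1, SAP Section 3 and the SAP schedule (Section 3.5) carry the same week-54 window.
- **Time since the last visit.** Section 10.1 describes "a follow-up visit at 2 weeks after the last visit".
- **Time since the last dose.** The Synopsis and Section 7.1 attach a second condition to the week-54 visit. In the Synopsis it reads "approximately 2 weeks after the last PH94B administration, to undergo C-SSRS, PWC-20, and vital signs assessments, and record AEs".

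Section 10.2 states the tolerance without naming a week: ±3 "days is permitted for Visit 3 and the follow-up visit (Visit 15"). Early terminators have a relative rule only: they "return to the clinic for a follow-up visit (Visit 15) approximately 2 weeks later" (Section 7.1).

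On the analysis side, SAP 6.1.5 assigns visits by nominal label. SAP 8.7 summarises PWC-20 for subjects with both Visits 14 and 15. SAP 8.1 splits treatment-emergent events into those before Visit 14 and those from Visit 14 onward.

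**The concern.** Visit 14 can move by two weeks either way, while Visit 15 is pinned to within three days of a fixed date. The distance between them therefore depends on where Visit 14 happens to fall, and at the edges it is nowhere near two weeks. No section gives an order of precedence.

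The distance matters for three safety outputs:

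- **PWC-20.** Scores after stopping PH94B are a listed safety endpoint. For subjects who finish treatment, Visit 15 is the only scheduled PWC-20 after treatment ends. Protocol 10.3.1.2.5 directs the questions to the week after stopping.
- **C-SSRS.** Visit 15 uses the since-last-visit version, so the gap sets its recall period.
- **Adverse events.** The gap sets the length of the SAP's second event period.

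Visits are labelled nominally and the interval is not summarised, so a reader of the tables could not tell a follow-up at 2 days from one at 30.

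**Working it through.** **Inputs** (Day 0 = Visit 2)

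- Visit 14: 52 × 7 ± 14 = 364 ± 14, Days 350 to 378, which is 29 permitted days (Section 2.2).
- Visit 15 by calendar: 54 × 7 ± 3 = 378 ± 3, Days 375 to 381 (Sections 2.2 and 10.2.4).
- Visit 15 by Section 10.1: Visit 14 + 14 days. That section gives no tolerance. I show 0, ±3 (borrowed from Section 10.2) and ±7 (my assumption).
- Longest screening period: 35 days.

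**The plan's own figure.** The Synopsis gives a maximum duration of about 59 weeks: (35 + 378)/7 = 413/7 = 59.0. It reproduces with Visit 15 on its nominal calendar day. At the upper edge of the window it is (35 + 381)/7 = 59.4.

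**Calendar rule against the two-weeks-after-Visit-14 rule.** With tolerance t, both can be met when Visit 14 + 14 − t ≤ 381 and Visit 14 + 14 + t ≥ 375, that is, for Visit 14 from Day 361 − t to Day 367 + t.

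| Tolerance | Compatible Visit 14 days | Count | Incompatible |
|---|---|---|---|
| exactly 14 days | 361–367 | 7 of 29 | 22 |
| 14 ± 3 | 358–370 | 13 of 29 | 16 (350–357 and 371–378) |
| 14 ± 7 (assumed) | 354–374 | 21 of 29 | 8 (350–353 and 375–378) |

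**Gap under the calendar rule alone** (375 − Visit 14 to 381 − Visit 14)

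| Visit 14 day | Gap to Visit 15, days |
|---|---|
| 350 | 25 to 31 |
| 357 | 18 to 24 |
| 364 | 11 to 17 |
| 371 | 4 to 10 |
| 378 | −3 to 3 |

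Visit 15 cannot precede Visit 14, so the permitted range is 0 to 31 days. The two windows overlap on Days 375 to 378. Reading 12 months as 365 days (Visit 14 on Days 351 to 379) leaves the 361–367 range unchanged and makes the extreme gaps 24 to 30 and −4 to 2 days.

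**Calendar rule against the last-dose rule.** This is a separate question, because dosing is as needed and the last dose may precede Visit 14.

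- Days off drug at Visit 15 are at least 375 − Visit 14. This exceeds 17 when Visit 14 is on or before Day 357 (8 of 29 days) and exceeds 21 when it is on or before Day 353 (4 of 29). In those cases the conflict is unavoidable.
- At the late end it can be avoided. At least 11 days off drug by Day 381 needs only a last dose on or before 381 − 11 = Day 370.

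**With Visit 15 at Visit 14 + 14 ± 3.** The gap is 11 to 17 days for every subject. Visit 15 falls between 350 + 11 = Day 361 and 378 + 17 = Day 395. Maximum duration becomes (35 + 378 + 14)/7 = 61.0 weeks, or (35 + 378 + 17)/7 = 61.4 with the tolerance.

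**The case against.** The best defence is that the intent can be recovered. The two-week interval appears in the Synopsis, Section 7.1 and Section 10.1. The amendment summary shows that Section 10.1 was deliberately changed from a week-54 visit to the relative rule, and Section 10.2 names no week. On that view week 54 is a leftover label, and a 0-day or 31-day gap needs a site to ignore half of a sentence. This shows which rule the sponsor probably wants. It does not remove the conflict: the schedule table and the Visit 15 section, which sites work from, still tie the ±3 days to week 54.

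A second argument is that the Synopsis caps treatment at 12 months. If dosing stops by about Day 365, Days 375 to 381 are at least 10 to 16 days off drug however late Visit 14 is. Anchoring on a Visit 14 at Day 378 would then push Visit 15 to Days 389 to 395, at least 24 to 30 days off drug. However, Section 7.1 ends treatment at Visit 14, window included, and Section 10.2.1.1 treats subjects up to Visit 14. The cap therefore does not settle the matter. It is still fair to say that time since last dose is the quantity of interest for withdrawal, and that anchoring on the visit does not control it.

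It is also true that the since-last-visit C-SSRS adapts to whatever gap occurs, that the affected summaries are descriptive, and that listings may let a reader work out the interval. These points limit the severity. They do not make the two rules compatible.

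**Conclusion.** The inconsistency is real and affects an operative visit rule. With a 14 ±3-day interval, 16 of 29 permitted Visit 14 days cannot satisfy both the calendar window and Section 10.1. Even at ±7 days, 8 cannot. Followed as written, the calendar window permits follow-up on the same day as end of treatment or a month later.

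The finding rests on Day 0 being Visit 2, on 52 and 54 weeks being Days 364 and 378, and on the stated tolerances. It applies to subjects who finish 12 months, not to early terminators. It also does not refer to the rollover group that the protocol calls Completers. The documents give no distribution of actual visit days, so the share of subjects affected is unknown. No test or decision rule depends on it. It should be corrected, but it does not threaten the study's main safety conclusions.

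**What to change.** Make the Section 10.1 rule operative: Visit 15 at 14 ±3 days after Visit 14 or early termination for all subjects, with week 54 kept only as a nominal label.

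- **Protocol:** edit the Synopsis, the Schedule of Events, Section 7.1 and Section 10.2.4. State in Section 10.2 that the ±3 days runs from Visit 14/ET + 14 days. Change the stated maximum duration from about 59 to about 61 weeks.
- **SAP:** conform Section 3 and the schedule in Section 3.5. In Section 8.7, derive days from Visit 14/ET to Visit 15 and report n, median, minimum and maximum beside the PWC-20 summary.

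The cost is a wording change in both documents, a maximum duration about two weeks longer, and one variable derived from dates already collected. The permitted gap narrows from 0–31 to 11–17 days. Time since last dose will still vary under as-needed dosing. For subjects whose visits have already taken place, reporting the interval is the part that still helps.

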### **10.3. Assessments**

#### **10.3.1 Safety Variables**

Safety assessments will include the evaluation of AEs, clinical laboratory assessments, vital signs, 12-lead ECGs, physical examinations, HAM-D17, C-SSRS evaluations, and the PWC-20.

##### **10.3.1.1 Clinical Laboratory Safety Assessments**

###### **10.3.1.1.1 Clinical Laboratory Tests to be Performed**

Samples for the following laboratory tests will be collected at the time points specified in the schedule of events ([Table 2-1](#)).

The following laboratory tests will be performed on site during the study:

- Urine pregnancy test (for all female subjects of childbearing potential)
- Urine drug screen

The following laboratory tests will be performed by the central laboratory during the study:

Hematology Panel: hematocrit, hemoglobin, mean corpuscular hemoglobin, mean corpuscular concentration, mean corpuscular volume, platelets, red blood cell count, white blood cell count with differential, red blood cell morphology

Hematology Differential Panel: basophils, eosinophils, lymphocytes, monocytes, neutrophils

**Serum Chemistry Panel:** alanine aminotransferase, aspartate aminotransferase, albumin, calcium, chloride, alkaline phosphatase, bicarbonate, cholesterol, creatine kinase, creatinine, direct bilirubin, lactate dehydrogenase, magnesium, globulin, glucose, gamma-glutamyl transferase, indirect bilirubin, phosphorous, potassium, sodium, total bilirubin, total protein, triglycerides, urea nitrogen, uric acid

**Urinalysis**  
**Macroscopic Panel:** bilirubin, blood, clarity, color, glucose, ketones, leucocyte esterase, nitrite, pH, protein, specific gravity, urobilinogen

**Urine Drug Screen:** If on-site urine drug screen is positive, urine sample will be submitted to central laboratory for confirmatory urine drug screen to be performed:  
opiates, cocaine, amphetamines, barbiturates, benzodiazepines, cannabinoids, methadone, phencyclidine, propoxyphene, methamphetamine, buprenorphine, ecstasy, and oxycodone

**Other:** thyroid stimulating hormone  
free thyroxine (T4) will automatically be performed if thyroid stimulating hormone level is above the upper or below the lower normal limits

The central laboratory should be used for any unscheduled and follow-up labs, if needed. Additional urine and blood samples may be collected for further evaluation of safety as warranted by the Investigator's judgment.

Results and reports from the central laboratory should be filed with the source documents for each subject. The central laboratory will provide laboratory results to the study site as soon as they are available; results will also be provided to the sponsor or designated data manager within agreed upon timelines.

Any laboratory value outside the normal range will be flagged for the attention of the Investigator, who must indicate whether or not the value is of clinical significance. If the result of any laboratory test performed during Screening is clinically significant, the subject should not be advanced to Visit 2 (Baseline) before discussing with the Medical Monitor. However, any abnormal result may be repeated to confirm the finding before excluding the subject from potential inclusion in the study. In addition, subjects should be excluded if they have any other abnormal laboratory test at Screening that, in the Investigator's judgment, is medically significant in that it would impact the safety of the subject, the conduct of the study, or the interpretation of the study results.

Follow-up/unscheduled laboratory tests may be performed on clinically significant abnormalities as indicated by the Investigator. Unscheduled laboratory tests may be repeated at any time at the discretion of the Investigator for appropriate medical care.

